4.1.1 Primary outcome

• Superiority of valproate compared to placebo on the Positive and Negative Syndrome Scale (PANSS) positive subscale at the 12-month visit [4].

The primary outcome is the positive subscale of the PANSS, which measures psychotic symptom severity. The PANSS is a clinician-rated scale that assesses psychotic (positive), negative and general symptom severity in schizophrenia. The PANSS psychotic (positive) rating at the end of the double-blind study (12 months) will serve as the main outcome measure [4]. The positive scale has seven items covering psychotic symptoms (delusions, conceptual disorganization, hallucinations, excitement, grandiosity, suspiciousness/persecution and hostility), each rated from 1 (absent) to 7 (very severe). The scale's reliability, criterion-related validity, and construct validity have been well documented [29].

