10.1 Sample Size

We have powered our study on the basis of superiority of valproate compared to placebo on the PANSS positive subscale using an effect size of 0.3. An effect size of 0.3 was selected as, in line with other trials of antipsychotic augmentation for treatment resistant schizophrenia, effects smaller than this are considered unlikely to be clinically meaningful [51, 52]. Assuming a two-sided significance level of 0.05 and 1:1 allocation, we will require 290 participants in the analysis dataset to detect an effect size of 0.3 with 90% power. This allows for a correlation between measures (at baseline and three follow-up points) of 0.4. An estimate of attrition of 20% across both arms for the primary end-point at 12 months requires a recruitment total of 362 participants at

baseline. The attrition rate of 20% is an estimate based on studies of antipsychotic augmentation using a similar design to our proposal, for example, the FOCUS study (Cognitive therapy augmentation of an antipsychotic for treatment resistance) had an attrition rate of ~10% over 21months [53] and the CHAT study (antipsychotic augmentation with a second antipsychotic) had an attrition rate <10% [54]. In this context, a study of a novel drug as an augmentation agent to antipsychotic treatment had a discontinuation rate of 29% at 12 months [55]. This study had a considerably larger burden of measures and higher levels of monitoring than our study. As such we expect our attrition and discontinuation rates to be in the range of 10-20% level in line with the other studies.

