10.3 Analysis

Statistical analysis will be done according to the predefined statistical analytical plan (SAP). There is no planned interim analysis unless the DMEC direct us to conduct one. Any deviations will be reviewed by the trial steering committee.

Statistical analysis

The primary analysis will use intention-to-treat principles by including all participants with outcome data in the arms to which they were randomized and follow the CONSORT 2010 statement. Baseline data will be presented using summary statistics with no testing for baseline differences. Treatment effects on the primary and secondary continuous outcomes will be estimated using linear mixed models fitted to outcome variables at all-time points. Fixed effects will be: diagnosis (schizophrenia/ schizoaffective); centre; baseline PANSS psychotic symptom severity rating; treatment; time (categorical); and time*treatment interactions. Marginal treatment effects will be estimated for outcomes at each time point and reported separately as adjusted mean differences in scores between the randomised groups with 95% confidence intervals and two-sided p-values. For binary outcomes, the same approach will be followed using logistic mixed models. All models will be estimated using maximum likelihood estimation, which allows for missing outcome data under the Missing At Random assumption. We may also use inverse probability weighting or multiple imputation to adjust for non-adherence to allocated treatment and other intermediate outcomes as predictors of future loss to follow-up.

Secondary analysis will include accounting for treatment switches from placebo to valproate arms using inverse probability of censoring weighting to estimate the average

treatment effect and longitudinal instrumental variable analysis to estimate the complier average causal effect.

Cost effectiveness evaluation

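### The primary mixed model gives baseline PANSS positive one slope for 3, 6 and 12 months; a baseline-by-time term would protect the 12-month contrast at almost no cost

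*Protocol*

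**What the plan says.** Protocol section 4.1.1 makes the 12-month score the endpoint: "The PANSS psychotic (positive) rating at the end of the double-blind study (12 months) will serve as the main outcome". Section 10.3 says that effects on the primary and the continuous secondary outcomes are "estimated using linear mixed models fitted to outcome variables at all-time points". Its fixed effects are diagnosis, centre, and then "baseline PANSS psychotic symptom severity rating; treatment; time (categorical); and time*treatment interactions". Time by treatment is the only interaction listed. The covariance structure is not given.

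On missing data, section 10.3 states: "All models will be estimated using maximum likelihood estimation, which allows for missing outcome data under the Missing At Random assumption". Inverse probability weighting or multiple imputation is mentioned only as something that may be used.

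Section 10.1 plans on a single correlation: "This allows for a correlation between measures (at baseline and three follow-up points) of 0.4". It expects 20% attrition at 12 months.

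**The concern.** Treatment may act differently at each visit in this model, but baseline severity may not. The fitted baseline slope is a compromise across visits. If baseline predicts the score less well as the year goes on, that compromise is too steep at month 12, where the primary outcome lies, and too shallow at month 3, where the main secondary outcome lies. Some weakening is plausible: follow-up lasts a year, and sections 4.2 and 5.7 let clinicians adjust, switch or add antipsychotics throughout.

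Two things would follow. The 12-month contrast would use the baseline information less than fully. And because maximum likelihood deals with data missing at random only when the mean model is right, a baseline imbalance among patients still observed at month 12 would be corrected by the wrong amount.

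**Working it through.** **Inputs from the protocol (10.1).** "Assuming a two-sided significance level of 0.05 and 1:1 allocation"; "290 participants in the analysis dataset to detect an effect size of 0.3 with 90% power"; correlation 0.4; 20% attrition, 362 recruited.

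**The plan's own figure.** For one unadjusted visit, n per arm = 2 × (1.960 + 1.282)² / 0.3² = 233.5. Multiplying by the variance factor for the mean of three follow-ups, (1 + 2 × 0.4)/3 = 0.60, gives 140.1, so 141 per arm or 282 in all, within 3% of 290. Then 290/0.8 = 362.5, in line with 362. (A single 12-month ANCOVA contrast has factor 1 − 0.4² = 0.84 and needs 394 analysed. That is a separate matter.)

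**Precision.** With unit variances and complete data, let r12 be the correlation of baseline with the 12-month score, and b the common slope, that is, the generalised-least-squares average of the visit slopes under an unstructured residual covariance. The variance of the 12-month contrast is proportional to

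- common slope: 1 − 2·b·r12 + b²
- visit-specific slope: 1 − r12²

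The protocol gives only the flat 0.4. The decaying patterns are assumptions, with follow-up correlations of 0.4 throughout.

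| Baseline correlation at 3/6/12 months | b | Common | Visit-specific | Excess variance |
|---|---|---|---|---|
| 0.4/0.4/0.4 (protocol) | 0.400 | 0.840 | 0.840 | 0% |
| 0.5/0.4/0.3 | 0.414 | 0.923 | 0.910 | 1.4% |
| 0.6/0.45/0.3 | 0.486 | 0.945 | 0.910 | 3.8% |
| 0.65/0.5/0.3 | 0.539 | 0.967 | 0.910 | 6.3% |

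The last three rows equal about 5, 13 and 21 of 362 patients, from 362 × (1 − visit-specific/common).

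A separate large simulation with about 20% dropout, rescaled to 362 patients, agrees. Under flat 0.4 the standard error is 0.1063 with or without the term. Under 0.5/0.4/0.3 it is 0.1116 without and 0.1106 with, a variance ratio of (0.1116/0.1106)² = 1.018, and power at 0.3 SD is about 0.77 either way. A steeper assumed pattern, 0.7/0.5/0.3 with follow-up correlations of 0.7/0.7/0.5, gives 0.1145 against 0.1086, about 11% more variance and power 0.75 against 0.79.

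**Bias.** Assumed: 181 per arm, true effect 0.30 SD, about 20% missing at 12 months, dropout log-odds rising by 0.7 per SD of baseline in the placebo arm only; 500 simulated trials per scenario.

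| Pattern | Common slope | With baseline by time | Difference |
|---|---|---|---|
| 0.5/0.4/0.3 | 0.315 | 0.296 | 0.019 |
| 0.6/0.45/0.3 | 0.327 | 0.296 | 0.031 |

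The Monte Carlo error of each mean is about 0.11/√500 = 0.005, so 0.296 is compatible with 0.30.

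The larger simulation gives about 0.03 SD for one-arm dependence under 0.5/0.4/0.3. Under its steep pattern it gives about 0.06 SD, and about 0.10 SD if dropout also runs in opposite directions by arm. With the added term and an unstructured covariance, bias stays within about 0.005 SD of zero in all of these. When dropout does not depend on baseline, or depends on it equally in both arms, neither model shows bias under any correlation pattern. Under flat 0.4, neither model shows bias under any of the dropout patterns.

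**The case against.** The strongest reply is that the listed model fits the protocol's own planning assumption. A constant 0.4 with equal variances means equal slopes, so the common slope is right, no precision is lost and the missing-at-random statement holds. The protocol contains no visit-specific correlations. This stands. A reader might infer that the 12-month contrast does lose precision and is not protected against dropout; the documents do not support either as fact.

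Second, the model constrains the slope and not the correlation: slope = correlation × SD at the visit / SD at baseline. If the spread of scores grows over time, falling correlations need not mean falling slopes. Correlations 0.5/0.45/0.4 with SDs 1/1.11/1.25 give slopes of about 0.5 at every visit and no loss. Correlations 0.5/0.4/0.3 with SDs 1/1.15/1.3 give 0.4% excess variance, not 1.4%. This also stands, so the percentages above hold only for equal variances.

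Third, bias needs both unequal slopes and dropout that relates to baseline differently by arm. The flow diagram expects the same 10–20% attrition in both arms, mainly from withdrawn consent, and section 4.2 keeps following patients who stop study medication. These points make the bias less likely but do not exclude it: equal dropout rates can still hide different kinds of patient leaving each arm.

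Fourth, the protocol defers to a statistical analysis plan that is not at hand and may add the term. But section 10.3 already names the fixed effects and an interaction, so the protocol line is worth amending in any case.

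**Conclusion.** The point holds as a low-cost robustness recommendation. As listed, the model has one baseline slope for three visits. Under flat 0.4 with equal variances this costs nothing. Under the assumed decaying correlations the 12-month variance is about 1% to 6% larger. With dropout that depends on baseline in one arm only, the bias is about 0.02 to 0.03 SD, or 7% to 10% of the 0.3 SD target and roughly a fifth to a quarter of a standard error of about 0.11. Its sign depends on which arm loses which patients. Larger figures appear only under the steeper assumed pattern or opposite dropout patterns in the two arms.

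It would go too far to call the missing-at-random sentence wrong. Like any such statement, it is conditional on the fitted mean model. The added term makes that condition easier to meet.

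**What to change.** In section 10.3, add *baseline PANSS positive × time (categorical)* to the fixed effects of the PANSS positive model. For each other continuous outcome, interact with time the same baseline covariate that enters that model as a main effect, and name it. As written, section 10.3 lists only the PANSS psychotic rating for all of these outcomes, so a general instruction to interact the baseline score with time would be ambiguous. Leave the other terms unchanged, and carry the same wording into the statistical analysis plan.

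The cost is 2 degrees of freedom per model and one line of text. No new data are needed, and under the protocol's flat 0.4 the standard error does not change (0.1063 either way with dropout unrelated to baseline).

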- The discontinuation of the intervention will be measured at the 3, 6-month and 1-year time points. We will also record the cause of discontinuation under the following categories: (i) lack of efficacy, (ii) adverse effects, (iii) switch to another antipsychotic (including clozapine), (v) lost to follow-up or (vi) personal reasons.
- We will evaluate on an annual basis the long-term symptomatic and functional outcomes beyond the 12-month period primarily using the HoNOS (Health of the Nation Outcome Scales) and service use (admission/crisis/home treatment/other service use) to determine outcomes after patients have finished the trial. HoNOS is a global clinical outcomes tool that is routinely collected across all mental health services in the NHS and can be accessed electronically [39].
- Number starting clozapine treatment

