5.7 Concomitant Medication

Subjects must be on a non-clozapine oral antipsychotic treatment for at least 6 weeks, that is dosed in accordance with its Marketing Authorisation (MA) and The Maudsley Prescribing Guidelines in Psychiatry, and at a stable dose for a minimum of 2 weeks at the time of screening. Depot neuroleptic dose must be stable for at least 2 treatment cycles or at least 30 days (whichever is longer) prior to the screening visit. Subjects who require an increase in dose of their background antipsychotic medication during the study will be permitted. As this is a pragmatic trial changes to antipsychotic dose and formulation will be permitted. Also, a switch to non-clozapine antipsychotic or addition of non-clozapine antipsychotics to the treatment regimen will be permitted. However, switch to a clozapine will lead to discontinuation of the study medication.

The following information will be recorded on the case report form (CRF) for all medication administered between screening and the end of study or at discontinuation Medication name, dose, frequency, route, start date, stop date and indication. Prior treatment with antipsychotic agents including depot neuroleptics will be recorded for at least 3 months prior to screening. Subjects who require treatment with a prohibited concomitant medication in the middle of the trial will be weaned off the study medication but we will continue to monitor their outcomes (based on the SmPC of both the antipsychotic as well as sodium valproate drugs).

Clinicians will be reminded of the potential adverse interactions, as mentioned in the SmPC for sodium valproate while prescribing other medications. Benzodiazepines and anticholinergic medication will be allowed along both arms during the screening and

after enrolment. Clinical teams will not be restricted in prescribing other medications but details of use (irrespective of the randomized arm) and follow-up will be recorded. A secondary /sensitivity analysis will be carried out to determine if this differs between treatment groups.

The date and time of the last dose taken prior to scheduled efficacy assessments must be recorded at each visit. Subjects should be encouraged to avoid taking sedative/hypnotic medications within 8 hours of scheduled efficacy assessments.

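### The logistic mixed model set for binary outcomes has no finite maximum for discontinuation if that outcome is coded as cumulative status at 3, 6 and 12 months

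*Protocol*

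**What the plan says.** Section 10.3 first sets the approach for continuous outcomes: "linear mixed models fitted to outcome variables at all-time points", with fixed effects for diagnosis, centre, "baseline PANSS psychotic symptom severity rating; treatment; time (categorical); and time*treatment interactions". It promises that "Marginal treatment effects will be estimated for outcomes at each time point". It then adds one general sentence: "For binary outcomes, the same approach will be followed using logistic mixed models". The next sentence says "All models will be estimated using maximum likelihood estimation". Section 10.3 names no binary outcome, no odds ratio and no random-effects structure.

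Section 4.1.2 lists the outcome that this rule most plainly reaches: "The discontinuation of the intervention will be measured at the 3, 6-month and 1-year time points". It also lists "Number starting clozapine treatment", without visit times. Section 4.2 counts a move to clozapine as discontinuation of the intervention.

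The summary of the analysis at the end of the Rationale mentions logistic models for dichotomous outcomes and does not call them mixed.

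**The concern.** A participant who has permanently stopped the study drug by 3 months has also stopped by 6 and 12 months. If the outcome at each visit is whether the participant has discontinued so far, the series never returns from 1 to 0. A logistic model with a normal participant intercept and finite variance always gives some probability to patterns such as 010 or 100. It can remove that misfit only by letting the variance grow without bound. Maximum likelihood then has no finite solution, and the participant-specific odds ratio grows with the variance.

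Discontinuation, with its recorded causes, shows how acceptable a year of augmentation is, and section 10.1 expects it in 10–20% of participants. An estimate set by the number of quadrature nodes and a convergence tolerance should not be reported for it.

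**Working it through.** The protocol gives no figure to reproduce here, so the check is on the behaviour of the likelihood.

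**Inputs.** From the protocol: 181 per arm (flow diagram), visits at 3, 6 and 12 months, free time-by-treatment effects, maximum likelihood. Assumed: a random participant intercept, cumulative coding, complete status data, and cumulative discontinuation of 8/13/20% (placebo) and 13/21/30% (valproate).

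**Model.** logit P(Y = 1 at visit t, arm g | u) = a(g,t) + σu, with u standard normal.

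**Upper bound.** The pattern probabilities 000, 001, 011, 111 are 0.80, 0.07, 0.05, 0.08 on placebo and 0.70, 0.09, 0.08, 0.13 on valproate. The saturated log-likelihood is 181 × Σ p ln p per arm:
- Placebo: 181 × (−0.7165) = −129.69
- Valproate: 181 × (−0.9337) = −169.00
- Total: −298.68

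When σ tends to infinity and the a(g,t) scale with it, each arm becomes a threshold model with three ordered cut-points, which reproduces any four such probabilities exactly. The bound is therefore approached in the limit. At any finite σ some probability is lost to impossible patterns, so the bound is never reached.

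**Profile over σ, fine-grid integration:**

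| σ | log-likelihood | conditional OR, 12 m | marginal OR, 12 m |
|---|---|---|---|
| 0.5 | −461.54 | 1.76 | 1.72 |
| 1 | −418.71 | 1.91 | 1.74 |
| 5 | −313.20 | 5.69 | 1.74 |
| 20 | −298.84 | 585 | 1.71 |
| 80 | −298.68 | about 1e11 | 1.71 |

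The assumed truth is (0.30/0.70)/(0.20/0.80) = 1.71.

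**Other data, same behaviour.** With 16.6% against 22.1% at 12 months, the log-likelihood rises from −377.41 (σ = 1) to −249.76 (σ = 100, the saturated value). The conditional log OR goes from 0.42 to 20.23, while the marginal OR stays at 1.43–1.46. On simulated data with the protocol's covariates, the log-likelihood rises from −403.15 (σ = 1) to −284.79 (σ = 40), and the log OR from 0.85 to 16.43.

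**Does a marginal summary rescue the fit?** I refitted the first example at σ = 40 with ordinary, non-adaptive Gauss–Hermite quadrature and computed the marginal 12-month OR with the same nodes:

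| nodes | marginal OR |
|---|---|
| 7 | 1.47 |
| 10 | 1.17 |
| 15 | 2.35 |
| 20 | 1.54 |
| 30 | 1.74 |

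Exact integration gives 1.71. At large σ the integrand is close to a step function, and a few nodes cannot represent it. Adaptive quadrature was not tried.

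**Models without a random intercept** are finite on the simulated covariate data:
- Logistic at 12 months: log OR 0.71 (SE 0.26)
- GEE at 3, 6 and 12 months: 0.55, 0.60, 0.73 (SE 0.37, 0.29, 0.27)
- Discrete-time hazard by interval: 0.54, 0.60, 0.87 (SE 0.36, 0.41, 0.46)

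**The case against.** The case for leaving the text alone has four parts.

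**Section 10.3 promises marginal effects, not a conditional odds ratio.** This is right, and the exactly integrated marginal risks are stable. A reader might infer that any odds ratio from this model is meaningless; that holds only for the conditional one. But section 10.3 describes the marginal report as adjusted mean differences in scores. It gives no standardisation step for a binary outcome, and the quadrature results show that an ordinary fit need not recover the stable value.

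**The coding is not fixed.** Scoring the first event in each interval among those still at risk gives a finite fit. That is a discrete-time hazard model, however, and not the mixed model named. The coding may be settled in a statistical analysis plan that is not at hand, but the protocol itself fixes the model class.

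**Off-drug status can reverse.** Section 6.5 allows drug holidays with later re-titration. With 4 reversals among 362 the maximum is finite, near σ = 10 on the grid, but the conditional log OR there is 2.04 against a marginal 0.35. Reversals restore a maximum without making the conditional coefficient a fair summary.

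**Clozapine start is not covered by name.** A reader might infer that the protocol prescribes a repeated-measures logistic model for it. The documents do not support this: it is listed as a number with no visit times. The point rests on discontinuation alone.

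**Conclusion.** The point holds in a conditional form. If discontinuation is coded as cumulative status at the three visits and fitted by maximum likelihood with a random participant intercept, there is no finite maximum. The conditional 12-month odds ratio diverges (1.8 to about 1e11 in the worked example), and the value printed depends on quadrature and convergence settings. The marginal odds ratio is finite under exact integration (1.71 to 1.74 in the table) but ranged from 1.17 to 2.35 under ordinary quadrature.

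This rests on the assumed event rates, the assumed random intercept and complete status data. The divergence does not depend on the particular rates, since it follows from the monotone patterns. It would be too strong to say that the plan can give no usable estimate of discontinuation: a carefully integrated marginal risk would be usable. The primary outcome and the other continuous outcomes are unaffected. The change is worth making because a stated rule is unreliable for a listed secondary outcome and the repair is nearly free.

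**What to change.** In section 10.3 and the analysis plan:

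- State how discontinuation is coded (cumulative status or first event per interval) and how drug holidays count.
- For discontinuation, and for clozapine start if it is modelled, use ordinary logistic regression of 12-month status adjusted for diagnosis, centre and sex. Report a standardised risk difference or marginal odds ratio with its confidence interval. If all three visits are wanted, use GEE.
- Add a time-to-event or discrete-time hazard analysis where dates allow. Section 5.7 records "Medication name, dose, frequency, route, start date, stop date and indication", which supports a clozapine start date. That section is about concomitant medication, so confirm that the case report form also captures the date on which study drug stopped.
- Keep logistic mixed models for binary outcomes that can reverse.
- Align the Rationale and section 10.3 on whether the logistic models are mixed.

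The cost is wording only, apart from confirming the study-drug stop date. No new visits or participants are needed.

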10.2 Randomisation

Randomization will be stratified by diagnosis (schizophrenia or schizoaffective), site and sex and a permuted block randomization will be used for each stratum.

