For the base-case models under both perspectives, we will compare costs and outcomes between the treatment arms at baseline, 3-month, 6- month and 12-months follow-up. In these models we will control for baseline costs (only in the cost analysis); centre; baseline PANSS psychotic symptom severity rating; treatment; time (categorical); and time*treatment interactions.

Bootstrapping with mixed effects models will be used to generate confidence intervals that can be used to capture parameter uncertainty around the estimates in the cost-

effectiveness analysis. The 1000 treatment effect replications from this bootstrapping process will be plotted on cost-effectiveness planes and used to construct cost-effectiveness acceptability curves (CEAC). We will use cost effectiveness acceptability curves (CEACs) to explore the nature of the trade-off faced by the decision-maker in situations where one treatment option is both more effective and costly than the other. In this case, the decision maker would need to consider if it is worth incurring the higher costs to improve outcomes. Using this approach, we will be able to show the likelihood of valproate plus continuing antipsychotic treatment arm being seen as cost-effective relative to the placebo plus continuing antipsychotic treatment arm given different (implicit monetary) values placed on incremental outcome improvements. Bootstrapping and regression analysis will be used to generate CEACs. We will also explore the sensitivity of the results to changes in key parameters and the analyses will be repeated. This will include the same control variables as those in the base-case model.

11 Trial Steering Committee

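### The base-case economic models list baseline as an outcome time point while also adjusting for it, and omit diagnosis: no bias, but a specification to correct

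*Protocol*

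**What the plan says.** All of this is in Protocol section 10.3, apart from the stratification statement.

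- **Time points of the economic models.** The cost-effectiveness part says of the base-case models: "we will compare costs and outcomes between the treatment arms at baseline, 3-month, 6- month and 12-months follow-up".
- **Covariates of the economic models.** The following sentence refers back to the same models and has them "control for baseline costs (only in the cost analysis); centre; baseline PANSS psychotic symptom severity rating; treatment; time (categorical); and time*treatment interactions". Nothing marks baseline as descriptive only.
- **Covariates of the clinical model.** The statistical analysis part states: "Fixed effects will be: diagnosis (schizophrenia/ schizoaffective); centre; baseline PANSS psychotic symptom severity rating; treatment; time (categorical); and time*treatment interactions". The clinical models are "linear mixed models fitted to outcome variables at all-time points"; this does not say whether baseline is one of them, so it does not settle the reading of the economic text.
- **Stratification.** Section 10.2 says: "Randomization will be stratified by diagnosis (schizophrenia or schizoaffective), site and sex".
- **Use of the results.** The ICER denominators are between-arm differences in change. Intervals, cost-effectiveness planes and acceptability curves come from 1000 bootstrap replications of mixed models. Sensitivity analyses keep the base-case covariates. The QALY is one area-under-the-curve value per patient.

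**The concern.** If baseline is a level of the time factor, the baseline row's response equals its covariate for cost in the cost model and for PANSS positive in the PANSS model. That row has a true slope of 1, whereas the follow-up rows have a slope equal to the baseline-to-follow-up correlation (with equal variances). One common slope has to serve both. The baseline row also has a much smaller residual variance than the others, although a random-intercept model assumes one residual variance throughout. A baseline cost row covers the time before study entry and cannot carry a treatment effect.

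Diagnosis is a second, separate matter. It is in the clinical model but not in the economic one, so the PANSS difference in the cost-per-point ICER would come from a different model than the trial's primary result.

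Cost-effectiveness is part of the main aim in section 4.1, so the model behind it should be stated without this ambiguity.

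**Working it through.** The plan gives no figure for these models, so there is none to reproduce. The check borrows the sample-size inputs.

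**Inputs from section 10.1:** 290 analysed at 1:1, hence 290/2 = 145 per arm; correlation 0.4 between baseline and the three follow-ups; effect 0.3 SD. **Assumed here:** SD 1 at every visit, compound symmetry, random intercept, complete data. Section 10.3 fixes no covariance structure.

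**1. Slope.** The covariate is constant within a patient. With balanced data the common slope is therefore the average covariance of the response rows with baseline.
- Follow-up rows only: 0.40.
- Baseline added as a fourth row: (1 + 3 × 0.4)/4 = 0.55.

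**2. True SE of the marginal 12-month contrast.** With slope b, the per-patient variance is v = 1 + b² − 2b(0.4), and SE = √(2v/145).
- b = 0.40: v = 0.84, SE = 0.108.
- b = 0.55: v = 1 + 0.3025 − 0.44 = 0.8625, SE = 0.109.
- Ratio √(0.8625/0.84) = 1.013, so the SE is 1.3% larger.

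**3. SE reported by the model.** The model averages variance over the rows. The baseline row has (1 − 0.55)² = 0.2025 and the three follow-up rows have 0.8625 each, so the average is (0.2025 + 3 × 0.8625)/4 = 0.6975. The reported SE is √(2 × 0.6975/145) = 0.098. Its ratio to the true SE is √(0.6975/0.8625) = 0.90, about 10% too small.

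**4. Time-by-treatment coefficient against baseline.** The term b × baseline is the same at every visit, so it cancels. What remains is an unadjusted change score with variance 2(1 − 0.4) = 1.20 and SE = √(2 × 1.20/145) = 0.129. The ratio √(1.20/0.84) = 1.195 means an SE 19.5% larger.

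**5. Simulation with the same inputs (true effect −0.30; 20,000 trials).**

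| 12-month contrast | Mean estimate | Observed SE |
|---|---|---|
| Follow-ups as outcomes, baseline as covariate | −0.301 | 0.106 |
| Baseline also an outcome row, marginal contrast | −0.301 | 0.108 |
| Same model, coefficient against baseline | −0.302 | 0.128 |

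In 150 random-intercept maximum-likelihood fits, the slopes were 0.40 and 0.55 for the first two rows. Mean model SEs were 0.107 and 0.098, against observed spreads of 0.106 and 0.107.

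**6. A chance baseline imbalance of one SE,** √(2/145) = 0.117 SD. Relative to the correct slope, the marginal contrast shifts by (0.55 − 0.40) × 0.117 = 0.018 SD, 6% of the 0.3 effect. The coefficient against baseline shifts by (1 − 0.40) × 0.117 = 0.070 SD, 23% of it.

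**7. Other correlations (assumed range 0.2 to 0.7).** The true SE of the marginal contrast is 2.1% to 0.5% larger, the model SE is 8% to 12% too small, and the coefficient against baseline has an SE 29% to 8.5% larger.

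**8. Diagnosis.** With schizoaffective share p and outcome difference d (in SD), the SE ratio from omission is √((0.84 + p(1 − p)d²)/0.84). The protocol gives neither p nor d. For p = 0.1, d = 0.2 the ratio is 1.002; for p = 0.4, d = 0.5 it is 1.035.

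**The case against.** The strongest reply is that the text never calls baseline a response row. The authors may intend only to report baseline values and adjust for them, and an analysis plan not shown may say so. That reading is possible. But the covariate sentence points back to the same models, and nothing in section 10.3 excludes the double use, so the wording still needs correcting.

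A second reply is that the harm is small, and this largely stands. The estimates are unbiased and the marginal contrast loses little precision. The economic intervals are to come from a bootstrap, which would largely repair the model-based SEs if participants are resampled; the protocol does not state the resampling unit. A difference in change can also be estimated by covariance adjustment, so the 19.5% loss depends on which coefficient is taken.

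Three stronger readings are tempting, and the documents do not support them.

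- A reader might infer a conflict with "Baseline data will be presented using summary statistics with no testing for baseline differences". The economic text speaks of comparing the arms and plans no baseline test.
- A reader might infer a type I error of about 8% for the ICER. That follows from the model-based SE in a 5% test, and the economic analysis plans neither.
- A reader might infer a fall in power from about 80% to about 64% for a 12-month contrast. That needs the change-score reading or a slope forced to 1, for example through an unstructured covariance that the protocol does not specify. The economic analysis is not powered in any case.

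On diagnosis, it is fair to reply that sex is also a stratification factor and is absent from both models. The point here is narrower: the two covariate lists differ without a reason given.

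**Conclusion.** The point holds as a minor specification fault. Taken literally, section 10.3 uses baseline twice in the base-case economic models and leaves out a factor that the trial stratifies by and includes in its clinical model.

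The consequence is a wrong baseline slope and some loss of precision, small for the marginal contrast and appreciable only if the coefficient against baseline supplies the difference in change. These sizes apply to PANSS positive and rest on the section 10.1 correlation plus the assumed covariance structure and complete data. Costs cannot be sized, because the protocol gives no cost SD and no correlation between baseline and follow-up costs. The QALY outcome has no baseline row, so the cost-per-QALY denominator is not touched by the double use.

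Omitting diagnosis causes no bias under stratified 1:1 allocation. Its main effect is that the PANSS difference in the ICER and the primary PANSS result come from different models.

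**What to change.** In the base-case paragraph of section 10.3:

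- Make 3, 6 and 12 months the modelled outcome times, with the baseline value as a covariate only, and report baseline costs and outcomes descriptively.
- Add diagnosis to the control list so that it matches the clinical model.
- Carry the same list into the bootstrap and sensitivity models.

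These are wording changes and need no new data. The added covariate costs one degree of freedom.
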